Clinical Trial Protocol

Document Number: c40535128-02	
EU Clinical Trial No.	2022-502424-43-00
BI Trial No.	1509-0001
BI Investigational Medicinal Product	BI 3000202
Title	A randomised, single-blind, placebo-controlled trial to investigate safety, tolerability, and pharmacokinetics of single rising doses of BI 3000202 administered as tablet to healthy male subjects, and a randomised, open-label, single-dose, two-way cross-over relative bioavailability comparison of BI 3000202 as tablet with and without food in healthy male subjects
Lay Title	A study in healthy men to test how different doses of BI 3000202 are tolerated and how food influences the amount of BI 3000202 in the blood
Clinical Phase	I
Clinical Trial Leader	[REDACTED]
Principal Investigator	[REDACTED]
Current Version, Date	Version 2.0, 25 May 2023
Original Protocol Date	21 Mar 2023
Page 1 of 84	
Proprietary confidential information © 2023 Boehringer Ingelheim International GmbH or one or more of its affiliated companies. All rights reserved. This document may not - in full or in part - be passed on, reproduced, published or otherwise used without prior written permission	

CLINICAL TRIAL PROTOCOL SYNOPSIS

Company name	Boehringer Ingelheim
Original protocol date	21 March 2023
Revision date	25 May 2023
BI trial number	1509-0001
Title of trial	A randomised, single-blind, placebo-controlled trial to investigate safety, tolerability, and pharmacokinetics of single rising doses of BI 3000202 administered as tablet to healthy male subjects, and a randomised, open-label, single-dose, two-way cross-over relative bioavailability comparison of BI 3000202 as tablet with and without food in healthy male subjects
Principal Investigator	[REDACTED]
Trial site	[REDACTED]
Clinical phase	I
Trial rationale	
This trial starts the clinical development of BI 3000202. The single rising dose (SRD) part of the trial investigates safety, tolerability, and pharmacokinetics of a range of single doses of BI 3000202 as basis for further development.
 
The food effect (FE) part is conducted to assess the effect of food on the relative bioavailability of the BI 3000202 [REDACTED].

Trial objectives	
SRD part: To investigate safety, tolerability, and pharmacokinetics following single rising doses of BI 3000202 as [REDACTED].
 
FE part: To investigate the influence of food on the relative bioavailability of the BI 3000202 [REDACTED].

Trial endpoints	
SRD part:
 
Primary endpoint: Occurrence of any treatment-emergent adverse event assessed as drug-related by the investigator. This is expressed as the percentage of subjects treated with investigational drug who experience such an event.Secondary endpoints: AUC₀₋₂₄ and C_{max} of BI 3000202 in plasma 
FE part:
 
Primary endpoints: AUC₀₋₂₄ and C_{max} of BI 3000202 in plasmaSecondary endpoint: AUC_{0-∞} of BI 3000202 in plasma
Trial design	
SRD part: Single-blind, randomised within dose groups, placebo-controlled parallel-group design.
 
FE part: Open-label, randomised, single-dose, two-way cross-over design investigating the two treatments: [REDACTED] fasted and [REDACTED] fed

Number of subjects total entered on each treatment	68* SRD part: 56* (6 receiving BI 3000202 and 2 receiving on placebo at each of 7 dose levels) FE part: 12 subjects (all on active) * Additional subjects may be entered in the SRD part to allow testing of additional doses based on experience gained during the trial conduct (e.g. preliminary PK data), provided the planned and approved highest dose will not be exceeded. Thus, the actual number of subjects entered in the SRD part may exceed 56 but is not to exceed 80. The addition of further dose groups exceeding the already tested dose levels for the evaluation of safety findings will be subject to a substantial CTP amendment requiring approval.
Diagnosis	Not applicable
Main inclusion criteria	Healthy male subjects, age of 18 to 45 years (inclusive), body mass index (BMI) of 18.5 to 29.9 kg/m ² (inclusive)
Test products Dose mode of administration	SRD part: [REDACTED] BI 3000202 FE part: [REDACTED] BI 3000202 SRD part:* [REDACTED] as single dose * Based on experience gained during the trial conduct (e.g. preliminary PK data), intermediate doses may be tested provided the planned and approved highest dose will not be exceeded. FE part:** [REDACTED] as single dose ** The FE part will only be started if in the SRD part a dose at least 4-fold the dose selected for the FE part has shown acceptable safety and tolerability. This means, that a dose of [REDACTED] to be used in the FE part requires a safe and tolerable dose of at least [REDACTED] in the SRD part. SRD part: [REDACTED] an overnight fast of at least 10 h FE part: [REDACTED] an overnight fast of at least 10 h (Treatment R) and following a high calorie, high fat breakfast (Treatment T)
Comparator products Dose mode of administration	SRD part: Placebo to BI 3000202 [REDACTED] FE part: Not applicable SRD part: [REDACTED] (placebo [REDACTED] matching to active dose groups) FE part: Not applicable SRD part: [REDACTED] after an overnight fast of at least 10 h FE part: Not applicable
Duration of treatment	SRD Part: 1 single dose FE part: 2 single doses separated by a washout period of at least 3 days

Statistical methods	
Descriptive statistics will be calculated for all endpoints.
 
SRD part: Dose proportionality will be explored under fasting conditions using a regression model. A 95% confidence interval for the slope will be computed.
 
FE part:
 
Relative bioavailability will be estimated by the ratios of the geometric means (tablet fed / tablet fasted) for the primary and secondary endpoints. Additionally, their two-sided 90% confidence intervals (CIs) will be provided. This method corresponds to the two one-sided t-test procedure, each at a 5% significance level. Since the focus is on estimation and not testing, a formal hypothesis test and associated acceptance range is not specified. The statistical model will be an analysis of variance (ANOVA) on the logarithmic scale including effects for sequence, subjects nested within sequences, period and treatment. CIs will be calculated based on the residual error from the ANOVA.

----------------------------	--

FLOW CHART – SRD PART

Visit	Day	Planned time (relative to drug administration) (h:min)	Approximate clock time of actual day (h:min)	Event and comment	Safety laboratory ⁸	PK blood ^{10,12}	PK urine ^{10,13}	PD blood ¹⁰	12-lead ECG ⁹	Continuous ECG monitoring	Vital signs (BP, PR)	Questioning for AEs and concomitant therapy ⁶
1	-21 to -1			Screening (SCR) ¹	x ^A				x		x	
2	-3 to -1	-74:00 ⁷	06:00	Ambulatory visit	x ^{B,7}							x
	1	-1:30	06:30	Admission to trial site ²								
		-1:00	07:00		x ⁵				x ^{2,9}	x ²	x ²	x ²
		-0:45	07:15						x ^{2,9}			
		-0:30	07:30	Allocation to treatment ²	x ^{C,2}	x ²	x ²	x ²	x ^{2,9}			
		0:00	08:00	Drug administration			▲			▲		
		0:15	08:15			x						
		0:30	08:30			x			x ⁹		x	x
		0:45	08:45			x						
		1:00	09:00			x		x	x ⁹		x	x
		1:30	09:30			x ¹¹			x ⁹			
		2:00	10:00	240 mL fluid intake		x		x	x ⁹		x	x
		2:30	10:30			x						
		3:00	11:00			x			x ⁹		x	x
		4:00	12:00	240 mL fluid intake, thereafter lunch ³		x	+	x	x ⁹	▼	x	x
		5:00	13:00			x						
		6:00	14:00			x		x	x ⁹			
		7:00	15:00	Snack (voluntary) ³								
		8:00	16:00			x	+	x	x ⁹		x	x
		10:00	18:00	Dinner ³								
		12:00	20:00			x	+		x ⁹		x	x
	2	24:00	08:00	Breakfast (voluntary) ³ , discharge from trial site	x ^C	x	▼	x	x ⁹		x	x
	3	48:00	08:00	Ambulatory visit		x		x ¹⁴	x ⁹		x	x
4	4 to 14			End of study (EoS) examination ⁴	x ^D				x		x	x

- Subject must be informed and written informed consent obtained prior to starting any screening procedures. Screening procedures include physical examination, check of vital signs, 12-lead ECG and rhythm strip over at least 15 min, safety laboratory (including drug screening and infectious serology), demographics (including determination of body height and weight, smoking status and alcohol history), medical history, concomitant therapy and review of inclusion/exclusion criteria. Pharmacogenetic samples will be collected if needed.
- The time is approximate; procedures are to be performed and completed within the 3 h prior to drug administration. Allocation to treatment may be performed at any time following enrolment but must be completed prior to drug administration.
- If several actions are indicated at the same time, the intake of meals will be the last action..
- At the end of study (synonym for End of Trial), the EoS examination includes physical examination, vital signs, ECG, safety laboratory, recording of AEs, and concomitant therapies.
- Urine drug screening and alcohol breath test only
- AEs and concomitant therapies will be recorded throughout the trial, but will be specifically asked for at the times indicated in the Flow Chart above.
- Safety laboratory to be taken and to be medically evaluated within 3 days prior to administration of study drug; this safety laboratory assessment can be omitted if the screening examination is performed on Days -3, -2 or -1.
- Letters A, B, C, and D describe different sets of safety laboratory examinations (see Table [5.2.3: 1](#))

9. The ECG recording must be performed in triplicate ECGs at this time. At baseline (Day 1 predose) 3 triplicate ECGs are recorded within approximately 1 h. The baseline recordings should be separated by about 15 min. The resulting ECGs will be transferred electronically to the central ECG lab.
10. Sampling times and periods may be adapted based on information obtained during the trial (e.g., due to preliminary PK or PD data) including addition of samples and ambulatory appointments if the total blood volume removed does not exceed 500 mL per subject
11. In dose group [REDACTED], one additional blood sample for stability testing will be taken at this time (refer to Section [5.3.2.4](#))
12. In dose group [REDACTED], including blood sample for metabolite identification (refer to Section [5.3.2.2](#))
13. A blank urine sample (x) is to be obtained prior to administration of trial medication. Other urine samples are to be collected over the stated post-dose intervals (◀—|—▶) 0-4, 4-8, 8-12, 12-24h.
14. For dose groups 6 and 7 only.

FLOW CHART – FE PART

Visit	Period	Day	Planned time (relative to drug administration) (h:min)	Approximate clock time of actual day (h min)	Event and comment	Safety laboratory ⁸	PK _{blood} ⁹	12-lead ECG	Vital signs (BP, PR)	Questioning for AEs and concomitant therapy ⁶
1		-21 to -1			Screening (SCR) ¹	X ^A		X	X	
2	1	-3 to -1	-74:00 ⁷	06:00	Ambulatory visit	X ^{B,7}				X ⁷
2/3 *	1/2 *	-1	-14:00	18:00	Admission to trial site ¹⁰	X ⁵				X
		1	-1:00	07:00	Allocation to treatment (visit 2 only) ²	X ^{C,2}	X ²	X ²	X ²	X ²
			-0:30	07:30	High fat, high calorie breakfast (treatment T only)					
			0:00	08:00	Drug administration					
			0:15	08:15			X			
			0:30	08:30			X			
			0:45	08:45			X			
			1:00	09:00			X			
			1:30	09:30			X	X	X	X
			2:00	10:00	240 mL fluid intake		X			
			2:30	10:30			X			
			3:00	11:00			X			
			4:00	12:00	240 mL fluid intake, thereafter lunch ³		X	X	X	X
			5:00	13:00			X			
			6:00	14:00			X			
			7:00	15:00	Snack (voluntary)					
			8:00	16:00			X			X
			10:00	18:00	Dinner ³					
			12:00	20:00			X			X
		2	24:00	08:00	Breakfast (voluntary) ³ , discharge from trial site	X ^C	X	X	X	X
		3	48:00	08:00	Ambulatory visit		X			X
4		4 to 14			End of study (EoS) examination ⁴	X ^D		X	X	X

*Two identical treatment periods separated by a wash-out phase of at least 3 days between BI 3000202 administrations

1. Subject must be informed and written informed consent obtained prior to starting any screening procedures. Screening procedures include physical examination, check of vital signs, 12-lead ECG, safety laboratory (including drug screening and infectious serology), demographics (including determination of body height and weight, smoking status and alcohol history), medical history, concomitant therapy and review of inclusion/exclusion criteria. Pharmacogenetic samples will be collected if needed.
2. The time is approximate; procedures are to be performed and completed within 3 h prior to drug administration. Allocation to treatment may be performed at any time following enrolment but must be completed prior to drug administration.
3. If several actions are indicated at the same time, the intake of meals will be the last action.
4. At the end of study (synonym for End of Trial), the EoS examination includes physical examination, vital signs, ECG, safety laboratory, recording of AEs, and concomitant therapies.
5. Urine drug screening and alcohol breath test only.
6. AEs and concomitant therapies will be recorded throughout the trial, but will be specifically asked for at the times indicated in the [Flow Chart](#) above.
7. Visit 2 only; safety laboratory to be taken and to be medically evaluated within 3 days prior to first administration of study drug; this assessment can be omitted if the screening examination is performed on Days -3, -2 or -1.
8. Letters A, B, C, and D describe different sets of safety laboratory examinations (see Table [5.2.3: 1](#))

9. Sampling times may be adapted based on information obtained during the trial (e.g., due to preliminary PK data in the SRD part) including addition of samples and ambulatory appointments if the total blood volume removed does not exceed 500 mL per subject
10. The time is approximate; all procedures are to be completed no later than 10 h prior to drug administration.

TABLE OF CONTENTS

TITLE PAGE	1
CLINICAL TRIAL PROTOCOL SYNOPSIS	2
FLOW CHART – SRD PART	5
FLOW CHART – FE PART	7
TABLE OF CONTENTS	9

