	Potassium	X	--	X	X
	Calcium	X	--	X	X

A: parameters to be determined at the screening examination

B: parameters to be determined at Visit 2 on Days -3, -2 or -1 (laboratory assessment can be omitted if screening examination is performed on Days -3, -2 or -1), for time point refer to [Flow Chart – SRD Part](#) and [Flow Chart – FE Part](#)

C: parameters to be determined on Day 1 (predose) and Day 2 of each treatment period (see Flow Chart - SRD Part and Flow Chart – FE Part)

D: parameters to be determined at the end of trial examination

Table 5.2.3: 1 Routine laboratory tests (cont.)

Functional lab group	BI test name (comment/abbreviation)	A	B	C	D
Urinalysis (Stix)	Urine Nitrite (qual)	X	--	X	X
	Urine Protein (qual)	X	--	X	X
	Urine Glucose (qual)	X	--	X	X
	Urine Ketone (qual)	X	--	X	X
	Urobilinogen (qual)	X	--	X	X
	Urine Bilirubin (qual)	X	--	X	X
	Urine HGB (qual)	X	--	X	X
	Urine Leucocyte esterase (qual)	X	--	X	X
	Urine pH	X	--	X	X
Urine sediment (microscopic examination if erythrocytes, leukocytes nitrite or protein are abnormal in urine)	Only positive findings will be reported (for instance, the presence of sediment bacteria, casts in sediment, squamous epithelial cells, erythrocytes, leukocytes)				

A: parameters to be determined at the screening examination

B: parameters to be determined at Visit 2 on Days -3, -2 or -1 (laboratory assessment can be omitted if screening examination is performed on Days -3, -2 or -1), for time point refer to [Flow Chart – SRD Part](#) and [Flow Chart – FE Part](#))

C: parameters to be determined on Day 1 (predose) and Day 2 of each treatment period (see Flow Chart - SRD Part and Flow Chart – FE Part)

D: parameters to be determined at the end of trial examination

The tests listed in Table [5.2.3: 2](#) are exclusionary laboratory tests that may be repeated as required. The results will not be entered in the CRF/database and will not be reported in the CTR. Except for drug screening, it is planned to perform these tests at screening only. Drug screening will be performed at screening and prior to drug administration(s).

Table 5.2.3: 2 Exclusionary laboratory tests

Functional lab group	Test name
Drug screening (urine)	Amphetamine/MDA
	Barbiturates
	Benzodiazepine
	Cannabis
	Cocaine
	Methadone
	Methamphetamines/MDMA/Ecstasy
	Opiates
	Phencyclidine
	Tricyclic antidepressants
Infectious serology (blood)	Hepatitis A antibodies (qualitative)
	Hepatitis B surface antigen (qualitative)

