	Hepatitis B core antibody (qualitative)
	Hepatitis C antibodies (qualitative)
	HIV-1 and HIV-2 antibody (qualitative)

To encourage compliance with alcoholic restrictions, a breath alcohol test (e.g. AlcoTrue® M, Blueprint Medical GmbH & Co. KG) will be performed prior to drug administration(s), and may be repeated at any time during the trial at the discretion of an investigator or designee. The results will not be included in the CTR.

Laboratory data will be transmitted electronically from the laboratory to the trial site.

It is the responsibility of the Investigator to evaluate the laboratory reports. Clinically relevant abnormal findings as judged by the Investigator are to be reported as adverse events (please refer to Section [5.2.6](#)).

In case the criteria for hepatic injury are fulfilled, several additional measures will be performed (please see Section [5.2.6.1.4](#)).

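### The laboratory set that must be medically evaluated in the 3 days before the first dose omits potassium, although QT prolongation is a listed product risk

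*Protocol*

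**What the plan says.** Screening, with laboratory set A, may take place on any of Days -21 to -1. The Flow Chart of the SRD part then requires at Visit 2 a "Safety laboratory to be taken and to be medically evaluated within 3 days prior to administration of study drug", with one exception: "this safety laboratory assessment can be omitted if the screening examination is performed on Days -3, -2 or -1". Footnote 7 of the FE Flow Chart repeats the rule for Visit 2 only: "safety laboratory to be taken and to be medically evaluated within 3 days prior to first administration of study drug".

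Section 5.2.3 identifies this sample as set B ("B: parameters to be determined at Visit 2 on Days -3, -2 or -1"). Set C follows: "C: parameters to be determined on Day 1 (predose) and Day 2 of each treatment period". Its nominal pre-dose time is -0:30 in the SRD part and -1:00 in the FE part. Footnote 2 of the SRD Flow Chart calls these times approximate and says that "procedures are to be performed and completed within the 3 h prior to drug administration"; the FE footnote is equivalent.

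On the handling of results, Section 5.2.3 says: "Laboratory data will be transmitted electronically from the laboratory to the trial site". It adds: "It is the responsibility of the Investigator to evaluate the laboratory reports". It gives neither a turnaround time nor a deadline relative to dosing.

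Table 1.4.2: 1 puts QT/QTc prolongation first among the product risks, on the basis of nonclinical data. Exclusion criterion 22 in Section 3.3.3 gives hypokalaemia as an example of a Torsade de Pointes risk factor.

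**The concern.** Set B is the plan's dedicated laboratory check shortly before first exposure, and the only one that carries an explicit duty of medical evaluation. It contains markers for the other product risks that Table 1.4.2: 1 monitors by laboratory test: bilirubin, lymphocytes, AST and ALT. For the QT risk, the one laboratory value that the protocol itself ties to Torsade de Pointes is missing from it.

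If the Day 1 set C result came back only after dosing, a potassium that had fallen since screening would become known too late to influence the decision to dose. What is at stake is the safety of individual subjects in a first-in-human trial. No estimate, interval or endpoint depends on it.

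**Working it through.** The plan states no figure to reproduce. The check is a comparison of the laboratory table with the timing and evaluation rules.

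**Step 1: what each set contains (Table 5.2.3: 1).**

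| Analyte | A: screening | B: Visit 2 | C: Day 1 pre-dose and Day 2 | D: end of trial |
|---|---|---|---|---|
| AST, ALT, CK, total and direct bilirubin, CRP | X | X | X | X |
| Potassium | X | -- | X | X |

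**Step 2: what must happen to each result before the first dose.**

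- Set B: taken and medically evaluated within 3 days before dosing.
- Set C: procedures performed and completed within 3 h before dosing. Evaluation of the result is not mentioned, although the set B footnote in the same Flow Chart does mention it.
- Any set: the investigator evaluates the reports, with no deadline before the dose.
- Section 8.3.1 requires documented evidence of eligibility before allocation to treatment. In both Flow Charts, allocation stands in the same row as the set C draw, and it may be done earlier. This check therefore does not force a reading of set C.

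**Step 3: who is concerned.** If screening falls on Days -3 to -1, set A may stand in for set B, and set A includes potassium, so there is no gap. The concern is limited to screening on Days -21 to -4.

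**Step 4: age of the last potassium certain to be known.** The Flow Charts place the Visit 2 sample at -74:00, clock time 06:00, for a dose at 08:00 on Day 1. As 74 h = 3 x 24 h + 2 h, this is 06:00 three calendar days earlier, which matches Day -3. There is thus no Day 0, and Day -d lies d days before the dose. Screening on Day -4 gives a value 4 days old, and on Day -21 a value 21 days old. For the analytes in set B the age is at most 3 days.

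**Step 5: number of extra tests.** At planned size there is at most one set B sample per subject: 56 SRD + 12 FE = 68. At the protocol's caps: 80 SRD + 12 FE + 4 FE replacements = 96. Each subject screened on Days -3 to -1 lowers the count by one if set B is omitted.

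**The case against.** The strongest reply is that potassium is in fact measured before every dose, in set C. The nominal draw time is approximate within a 3 h window, the trial runs in the sponsor's own Phase I unit, and a generous reading of a completed procedure could include review of the result. Section 3.1 adds that an SRD subject is dosed only in the absence of any safety concern. The protocol also addresses QT risk directly: exclusion of prolonged QTc and of QT-prolonging drugs, pre-dose ECGs in both parts (three triplicates in the SRD part), continuous monitoring to 4 h in the SRD part, and stopping criteria. The subjects are healthy men aged 18 to 45, and Section 1.4.3 does not regard the compound as high-risk.

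All of this stands, and it makes harm unlikely. It does not close the gap. The separately required evaluation of set B shows that the plan does not rest its pre-dose laboratory check on set C alone. The protocol also lists QTc prolongation (criterion 21) and hypokalaemia (criterion 22) separately, so a normal ECG does not stand in for a potassium value.

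A second reply is that the more direct remedy is a sentence requiring the set C potassium to be read before dosing. This has merit and would also reach the second FE dose, but it works only if results return in time, and the documents do not say whether they do.

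Some stronger readings are tempting and are not supported:

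- A reader might infer that subjects will be dosed on an unreviewed potassium. Site procedures and turnaround are not visible, so the documents do not show this.
- A reader might add calcium, which set B also omits. Nothing in the documents links calcium to the QT risk.
- A reader might count the doses concerned. The distribution of screening days and the frequency of unread set C results are both unknown. Any such count would reflect assumptions, and the true number could be zero.
- A reader might call this a contradiction. It is not: a reduced set B followed by a full set C is a coherent scheme with one weak spot.

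**Conclusion.** The point holds as a modest gap in the pre-dose safety check. For subjects screened on Days -21 to -4, the last potassium certain to be known before the first dose may be 4 to 21 days old, while the analytes in set B are at most 3 days old. The conclusion rests on the absence of any text requiring the set C result before dosing; a site procedure that ensures this would remove the gap in practice. The likelihood of harm is low, and no endpoint or analysis is affected. It is worth considering because the remedy is cheap and the protocol itself names both the risk and the risk factor.

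**What to change.** Mark potassium in column B of Table 5.2.3: 1 and run it on the set B chemistry sample. No new threshold is needed, because exclusion criterion 3 already covers out-of-range values that the investigator considers clinically relevant.

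The cost is at most 68 extra potassium results at planned size, or 96 at the caps. No extra visit is needed. No extra blood draw is needed either if the tube used for AST, ALT, CK and bilirubin also suits potassium; the tube type is not stated, so this is an assumption. The downsides are a small assay cost and an occasional repeat test.

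The change does not cover FE Period 2, because set B is not repeated there. A set C potassium from Day 2 of Period 1 does exist: at the minimum washout of 3 days it was drawn 3 - 1 = 2 days before the second dose, and earlier if the washout is longer. If the sponsor also wants an assured recent value for that dose, it would have to require review of the pre-dose set C potassium, provided that turnaround allows.
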